7.5.5.1. Anti-drug Antibodies

Serum samples will also be collected at scheduled time points prior to dosing to evaluate ADAs.

7.5.5.2. Pregnancy Screen

A serum pregnancy test will be performed for women of child bearing potential (WOCBP) at Screening/Baseline. A urinary pregnancy test will be performed any time pregnancy is suspected, and in accordance with the SOA. Urine pregnancy test may also be performed more frequently (monthly) based on local country requirements. The results of the pregnancy test must be known prior to administration of study drug. Patients who are pregnant are not eligible for study participation. Patients determined to be pregnant while on study will be followed until the pregnancy outcome is known (see Section 8.10).

7.5.6. Ophthalmologic Examination

An ophthalmologic examination will be performed at Screening/Baseline and in accordance with the Table 1-1. Patients are not required to repeat the ophthalmologic examination if the assessment was performed within 90 days of randomization. Visual acuity should be evaluated at the beginning of each specified visit (ie, prior to slit-lamp examination). Manifest refraction will be performed at each specified visit, where possible, prior to visual acuity testing and will be used to obtain a correction for visual acuity evaluations. Visual acuity testing should be done with best (most recent) correction and be tested in bright and dim light conditions.

Further details regarding the ophthalmologic examinations will be provided in the Site Operations Manual.

7.5.7. Concomitant Medications

All medications the patient receives during the Screening/Baseline period through the Follow-up Visit will be recorded. The indication for the medication must be assessed to determine if a new AE is present. See Section 5.1 for more details on prohibited and acceptable concomitant medications.

7.5.8. Adverse Events

Starting on Day 0, adverse events will be assessed and recorded. The reporting guidelines are provided in Section 8.

7.6. Other Assessments

7.6.1. Exploratory Biomarkers

Where local regulations permit, blood samples will also be collected at scheduled time points prior to dosing to evaluate exploratory biomarkers (mutant: WT TTR levels and additional cardiac and hepatic-derived proteins that may include galectin 3 and ST2). Aliquots of plasma and serum samples will be taken and frozen, to permit testing of the effect of ALN-TTRSC on the expression of these exploratory biomarkers.

Collection of samples for exploratory biomarker analysis will be subject to discretionary approval from each site's IRB/IEC. Samples will be stored by the Sponsor or designee in a secure and controlled environment until analysis, and will be destroyed by the Sponsor or designee after all worldwide obligations have been met, or sooner if required by local regulations.

7.6.2. DNA Sample

Where local regulations permit and subject to discretionary approval from each center's IRB/IEC, a voluntary blood sample for DNA extraction will be collected from each patient at Screening/Baseline. The voluntary DNA sample should only be obtained once during Screening. The results may be used as part of a later analysis, which could include a determination of the spectrum of TTR mutations in patients with ATTR and the relationship between TTR gene mutation and the safety and efficacy of ALN-TTRSC. The Sponsor will only analyze DNA sequences within genes relevant to the mode of action and response to ALN-TTRSC. No additional testing will be performed on the samples collected in the study.

DNA samples will be stored by the Sponsor, or designee, in a secure, monitored, and controlled environment until analysis, and will be destroyed by the Sponsor after all worldwide obligations have been met, or sooner if required by local regulations.

7.6.3. Pharmacoeconomics Questionnaire

Disease burden and healthcare utilization will be assessed using a patient reported pharmacoeconomics questionnaire.

8. ADVERSE AND SERIOUS ADVERSE EVENTS

8.1. Adverse Events Definition

An AE is any untoward medical occurrence in a patient or clinical investigational patient administered a pharmaceutical product and which does not necessarily have a causal relationship with this treatment.

An AE can therefore be any unfavorable and unintended sign (including an abnormal laboratory finding, for example), symptom, or disease temporally associated with the use of a medicinal product, whether or not considered related to the medicinal product.

All injection site reactions will be recorded as AEs.

8.1.1. Adverse Events of Clinical Interest

The following events are considered to be AEs of clinical interest:

- ISRs
- Hepatic AEs, including LFT abnormalities considered clinically significant by the Investigator

8.2. Serious Adverse Event (SAE) Definition

An SAE is any untoward medical occurrence that at any dose:

- Results in death
- Is life-threatening (an event which places the patient at immediate risk of death from the event as it occurred. It does not include an event that had it occurred in a more severe form might have caused death)
- Requires in-patient hospitalization or prolongation of existing hospitalization
- Results in persistent or significant disability or incapacity
- Is a congenital abnormality or birth defect
- An important medical event that may not be immediately life-threatening or result in
 death or hospitalization but may jeopardize the patient and may require intervention to
 prevent one of the other outcomes listed in the definition above (e.g. events include
 allergic bronchospasm requiring intensive treatment in an emergency room or at home,
 blood dyscrasias, convulsions, or the development of drug dependency or abuse).

8.3. Eliciting Adverse Event Information

The patient should be asked about medically relevant changes in his/her health since the last visit. The patient should also be asked if he/she has been hospitalized, had any accidents, used any new medications, or changed concomitant medication routines (both prescription and OTC).

In addition to patient observations, AEs will be documented from any clinically relevant laboratory findings, physical examination findings, ECG changes, or other findings that are relevant to patient safety.

8.4. Adverse Event Reporting

The Investigator is responsible for reporting all AEs that are observed or reported after the first dose of study drug regardless of their relationship to study drug through the end of the reporting periods defined in Section 8.5.

Any medical condition that is present when a patient is screened and does not deteriorate should not be reported as an AE. However, if it does deteriorate at any time after the first dose of study drug, it should be reported as an AE.

All AEs must be fully recorded in the site's source records and in the patients' eCRF, whether or not they are considered to be drug-related. Each AE should be described in detail: onset time and date, description of event, severity, relationship to investigational product, action taken, and outcome (including time and date of resolution, if applicable).

For AEs that are considered AEs of clinical interest, additional clinical information may be collected based upon the severity or nature of the event. If a patient has ISRs meeting any of the following criteria, the Investigator, or delegate, should contact the Medical Monitor and submit a supplemental ISR eCRF:

- ISRs that are recurrent and/or demonstrate a pattern of increasing severity
- Any ISR that is determined to be severe and/or a cause for study drug discontinuation
- Any ISR which, in the opinion of the Investigator, requires further medical evaluation or treatment

In some cases, where it is medically appropriate, further evaluation may include photographs, referral to a dermatologist, skin biopsy, or other laboratory testing. If a biopsy was obtained, the Sponsor may request that the biopsy also be reviewed by a central dermatopathologist.

For patients with hepatic AEs, local laboratory results may be collected to monitor LFT levels or other laboratory parameters.

Refer to the CRF completion guidelines for details on reporting events in the supplemental AE of
clinical interest eCRF form(s). When the form(s) is/are completed,
personnel will be notified electronically and may

follow-up with queries.

8.5. Adverse Event Reporting Period

AEs and SAEs will be reported according to the following timeframes:

 For patients who complete the study, AEs will be assessed through the End of Study Visit, Week 82. All AEs that occur after the start of study drug administration on Day 0 must be reported in detail on the appropriate eCRF page and followed to satisfactory resolution, or through the End of Study Visit after the last dose of study drug administration. Serious AEs will be followed through the End of Study Visit, or

until satisfactory resolution, or until the SAE is considered by the Investigator to be chronic or the patient is stable.

For patients who withdraw from the study early, ongoing AEs will be followed until
resolution or 28 days from last dose, whichever occurs first. Serious AEs will be
followed through 28 days from the last dose of study drug, or until satisfactory
resolution, or until the SAE is considered by the Investigator to be chronic or the
patient is stable.

8.6. Assessment of Causality

Causal relationship assessment to drug treatments is required for purposes of reporting AEs. To promote consistency, the following guidelines should be taken into consideration along with good clinical and scientific judgment when determining the relationship of drug treatments to an AE:

Definitely Related: A clinical event, including laboratory test abnormality, occurring in a

plausible time relationship to the medication administration, and which cannot be explained by concurrent disease or other drugs or chemicals. The response to withdrawal of the drug should be clinically plausible.

Possibly Related: A clinical event, including laboratory test abnormality, with a reasonable

time sequence to the medication administration, but which could also be explained by concurrent disease or other drugs or chemicals. Information

on the drug withdrawal may be lacking or unclear.

Unlikely Related: A clinical event, including laboratory test abnormality, with little or no

temporal relationship to medication administration, and which other drugs, chemicals, or underlying disease provide plausible explanations.

Not Related: A clinical event, including laboratory test abnormality that has no

temporal relationship to the medication or has more likely alternative

etiology.

8.7. Assessment of Severity

Adverse events are to be graded according to the categories detailed below:

Mild: Mild events are those which are easily tolerated with no disruption of

normal daily activity.

Moderate: Moderate events are those which cause sufficient discomfort to interfere

with normal daily activities.

Severe: Severe events are those which incapacitate and prevent usual activity.

Changes in severity should be documented in the medical record to allow assessment of the duration of the event at each level of severity. Adverse events characterized as intermittent

require documentation of the start and stop of each incidence. When changes in the severity of an AE occur more frequently than once a day, the maximum severity for the experience that day should be noted. If the severity category changes over a number of days, then those changes should be recorded separately (with distinct onset dates).

8.8. Coding of Adverse Events

The Medical Dictionary of Regulatory Activities (MedDRA) will be used to code AEs.

8.9. Serious Adverse Event Reporting

An assessment of the seriousness of each AE will be made by the Investigator. Any AE and laboratory abnormality that meets the seriousness criteria above (Section 8.2) must be reported to the CRO within 24 hours from the time that site personnel first learn of the event. All SAEs must be reported regardless of the relationship to study drug.

The initial report should include at least the following information:

- Patient's study number
- Description and date of onset of the event
- · Criterion for serious, and
- Preliminary assignment of causality to study drug

To report the SAE, complete the paper SAE form and fax it to provided in the Site Operations Manual) within 24 hours of awareness. SAE information must also be entered into the EDC system on the Adverse Events page within 5 calendar days of awareness.

Follow-up information must be provided to using the paper SAE report (fax number is provided in the Site Operations Manual) within 24 hours of the information becoming available. The Investigator should also submit any supporting documentation such as a patient discharge summary or autopsy reports. Updated/follow-up SAE information must also be entered into the EDC system on the Adverse Events page within 5 calendar days of receiving the information.

Appropriate remedial measures should be taken by the Investigator using his/her best medical judgment to treat the SAE. These measures and the patient's response to these measures should be recorded. All SAEs, regardless of relationship to study drug, will be followed by the Investigator until satisfactory resolution or the Investigator deems the SAE to be chronic or stable. Clinical, laboratory, and diagnostic measures should be employed by the Investigator as needed to adequately determine the etiology of the event.

8.9.1. Notifying the IRB/IEC

SAEs will be reported to the IRB/IEC per their institutional policy by the Investigator or Sponsor (or Sponsor designee) according to country requirements. Copies of each report and documentation of IRB/IEC notification and acknowledgement of receipt will be kept in the Investigator's study file.

8.9.2. Sponsor Reporting: Notifying Regulatory Authorities

The Sponsor or its representative is required to report certain study events in an expedited manner to the FDA, the European Medicines Agency's EudraVigilance electronic system according to Directive 2001/20/EC, and to all country Regulatory Authorities where the study is being conducted, according to local applicable regulations.

The following describes the safety reporting timeline requirements for suspected unexpected serious adverse reactions (SUSARs) and other reportable events:

Immediately and within 7 calendar days

 Any suspected adverse reaction that is: associated with the use of the study drug, unexpected, and fatal or life threatening. Follow-up information must be reported in the following 8 days.

Immediately and within 15 calendar days

- Any suspected adverse reaction that is: associated with the use of the study drug, unexpected, and serious, but not fatal or life threatening, and there is evidence to suggest a causal relationship between the study drug and the reaction.
- Any finding from tests in laboratory animals that: suggest a significant risk for human subjects including reports of mutagenicity, teratogenicity, or carcinogenicity.
- Any event in connection with the conduct of the study or the development of the study drug that may affect the safety of the trial subjects.

In addition, periodic safety reporting to regulatory authorities will be done by the Sponsor or its representative according to national and local regulations.

8.9.3. Sponsor Reporting: Notifying Participating Investigators

All Investigators will be informed by the Sponsor or its representative of relevant clinical safety findings from this or other clinical studies, as well as any new findings from tests in laboratory animals that significantly impact the benefit/risk to patients in this study. All reports should be transmitted to the IEC/IRB that approved the study.

8.10. Pregnancy Reporting

A female patient with a positive pregnancy test at Screening/Baseline is ineligible for this study. If a female patient becomes pregnant during the course of this study (or during the first month following the last dose of study drug), the patient must be instructed to stop all study drug administration, and the Investigator must report the pregnancy to the CRO within 24 hours of being notified of the pregnancy. Details of the pregnancy will be recorded on the pregnancy reporting form. The patient should receive any necessary counseling regarding the risks of continuing the pregnancy and the possible effects on the fetus.

The pregnancy should be followed by the Investigator until completion. At the completion of the pregnancy, the Investigator will document the outcome of the pregnancy. If the outcome of the

pregnancy meets the criteria for an SAE (i.e., postpartum complication, spontaneous abortion, stillbirth, neonatal death, or congenital anomaly), then the Investigator should follow the procedures for reporting an SAE as outlined in Section 8.9.

Pregnancy occurring in the partner of a patient participating in the study should also be reported to the Investigator, who will then report this to the CRO and follow to outcome as described above.

9. STATISTICS

9.1. Sample Size

For the 6-MWT primary endpoint, a sample size of 180 with a 2:1 treatment allocation (N=120 on ALN-TTRSC and N=60 on placebo) has 90% power to detect a treatment difference of 0.55 standard deviations using a Finkelstein and Schoenfeld analysis with a significance level of 0.05. 10.2 This assumes 20% of placebo patients and 13% of ALN-TTRSC patients die before the 18 month assessment (ie, Hazard Ratio [HR]=0.6). Assuming a standard deviation of 70 meters in change from baseline, this would correspond to 90% power to detect a treatment effect of 39 meters in the 6-MWT. Assuming a 10% patient dropout rate, approximately 200 patients will be enrolled in the study. Note that power for the comparison of percent reduction in serum TTR between treatment groups is expected to be >90% for a significance level of 0.05; sustained knockdown of serum TTR levels >85% has been observed in healthy volunteers and patients receiving ALN-TTRSC (Section 1.3). For this reason, overall power to establish efficacy is expected to be approximately 90% under the assumptions described above.

9.2. Statistical Methodology

A full statistical analysis plan will be finalized prior to database lock.

9.2.1. Populations to be Analyzed

The following patient populations (i.e., analysis sets) will be evaluated and used for presentation of the data:

- Modified intent to treat (mITT) population: all patients who were randomized and received at least 1 dose of ALN-TTRSC or placebo.
- Per protocol (PP) population: all patients who did not have any major protocol violations; and completed the 18-month 6-MWD assessment or died on-study.
- Safety population: All patients who received at least 1 dose of ALN-TTRSC or placebo (analyzed as treated, not as randomized).

The primary population for efficacy analyses will be the mITT population; the key efficacy results will also be analyzed for the PP population. For efficacy analyses, patients will be grouped according to the treatment to which they were randomized. The primary population for safety analysis will be the safety population. Patients will be grouped according to treatment received for summaries of safety.

9.2.2. Baseline Evaluations

Demographic and baseline disease characteristic data will be summarized. Data to be tabulated will include sex, age, and race, as well as disease-specific information.

9.2.3. Efficacy Analyses

9.2.3.1. Primary Efficacy Endpoint

There are two co-primary endpoints. The first co-primary endpoint is change from baseline (in meters) for a 6-MWD conducted 18 months after randomization. The primary efficacy analysis for the comparison of 6-MWD between treatment groups will be conducted using Wilcoxon Mann Whitney-based test statistics that will take into account informative missingness due to death and the loss of the ability to perform the test. Briefly, in this stratified non-parametric rank sum analysis, all pairs of patients within a stratum are compared. A pair of patients is compared first on time to death (if death occurs before 18 months); second on time until the inability to perform the test (if it cannot be determined as to which patient in a pair lived longer); and third on the change from baseline in 6-MWD at the time of the last assessment shared by both patients (if it cannot be determined as to which patient in a pair lived longer and which retained the ability to perform the 6-MWD longer). The analysis will be stratified based on the stratification parameters that are used for randomization.

The second co-primary endpoint is percent reduction from baseline in serum TTR using enzyme-linked immunosorbent assay. The area under the effect curve (eAUC) for percent reduction from baseline in serum TTR over time, where the y-axis is percent reduction and the x-axis is time since randomization, will be compared across groups using Analysis of Covariance (ANCOVA), in which the stratification variables and baseline serum TTR level will be included in the model as covariates. The eAUC will be computed using the trapezoidal method, where assessments missing due to death or discontinuation will be imputed using the baseline level, i.e., the percent reduction will be assumed to be 0%.

The study will have demonstrated efficacy if the p-value for each of the co-primary endpoints is \leq 0.05 (2-sided).

Sensitivity analyses for each co-primary endpoints, including different methods for handling of the missing data, will assess the robustness of the primary analysis for the mITT population.

9.2.3.2. Secondary Efficacy Endpoints

The secondary composite of CV mortality and CV hospitalization, as well as change in NYHA class and change in KCCQ, will also be compared across treatment groups using stratified Finkelstein and Schoenfeld Joint Rank Tests. CV mortality and all-cause mortality will be compared across treatment groups using stratified log-rank tests. CV hospitalizations will be compared using the stratified Anderson-Gill model for recurrent events. Analyses will be stratified using the stratification parameters that are used for randomization.

Type I error control for secondary endpoints will be achieved by a hierarchical ordering procedure. Endpoints will be compared across treatment groups in the following pre-specified order:

- Composite CV mortality and CV hospitalization
- New York Heart Association (NYHA) class (Appendix 1)
- Kansas City Cardiomyopathy Questionnaire (KCCQ)

- Cardiovascular (CV) mortality
- CV hospitalization
- All-cause mortality

If and only if a comparison is significant at p<0.05, the next endpoint in the hierarchy may be formally tested.

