3. INVESTIGATIONAL PLAN

3.1. Overall Study Design

This is a multicenter, multinational, randomized, double-blind, placebo-controlled Phase 3 study designed to demonstrate the clinical efficacy and safety of ALN-TTRSC in patients with TTR mediated FAC.

Approximately 200 consented eligible patients will be randomized to receive either ALN-TTRSC or placebo at a 2:1 ratio (ALN-TTRSC to placebo) in a blinded manner as a subcutaneous administration. Treatment groups will be balanced at randomization for NYHA classification (I and II versus III), TTR mutation (V122I versus other FAC mutations), and 6-MWD (≤325 meters versus >325 meters). Patients will receive ALN-TTRSC or placebo daily for 5 days during the first week, a single dose on Day 7, and then once weekly for 18 months.

Patients will undergo efficacy and safety assessments at Screening/Baseline, each month for first 3 months, and then at 3-6 month intervals.

The duration of patient participation in this study is approximately 20 months (inclusive of up to a 45 day Screening/Baseline window and up to 35 days of follow-up after the last dose).

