7.6 Efficacy

All efficacy analyses will be performed on the mITT population. In addition, the analysis of the coprimary efficacy endpoints will be also be evaluated using the PP population.

Where appropriate, analyses will be stratified based upon a subset of stratification parameters used for randomization: TTR mutation (V122I versus other FAC mutations), and 6-MWD (≤325 meters versus >325 meters). The values of these stratified parameters will be based upon the data entered in the eCRF.

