7.6.2.2 Change in NYHA from Baseline

The primary analysis of change in NYHA from baseline will be based on stratified Finkelstein and Schoenfeld Joint Rank Test. All pairs of patients will be compared within a stratum. A patient will be compared with another patient in a step-wise fashion to identify the patient in the pair with the better outcome:

Step 1: Compare time to death;
If it cannot be determined which patient lived longer, then go to Step 2

Step 2: Compare change in NYHA from baseline to the latest common study visit

Details of the comparisons of time to death and change in NYHA are described in Appendix I.

Descriptive statistics displaying a shift table of baseline NYHA class category [range: 1-4] to each post-baseline visit categories [range: 1-4] will be generated. An overall shift of the baseline to worst post-baseline NYHA class category will be presented as well for each treatment group.

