7.6.2.3 Change in overall summary score from Baseline - KCCQ

The primary analysis of change in overall summary score from baseline will be based on stratified Finkelstein and Schoenfeld Joint Rank Test. All pairs of patients will be compared within a stratum. A patient will be compared with another patient in a step-wise fashion to identify the patient in the pair with the better outcome:

Step 1: Compare time to death;

If it cannot be determined which patient lived longer, then go to Step 2

Step 2: Compare change in overall summary score at the latest common study visit

Note: The overall summary score is calculated based on responses from the KCCQ questionnaire. The questionnaire summarizes 8 subscales and 2 summary scores (see Appendix III for further details).

Details of the comparisons of time to death and change in overall summary score are described in Appendix I.

Descriptive statistics of overall summary score and change in overall summary score will be generated for each treatment group at baseline and each post-baseline visit. These analyses above will be repeated for each of the 8 subscales and clinical summary score used in the KCCQ questionnaire.

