Step 1: Comparison based on time to death

This comparison will use the same assumptions as stated for the co-primary endpoint.

Step 2: Comparison change in NYHA class from baseline

Definition of change in NYHA class from baseline: Change in NYHA class from baseline is defined as: (NYHA class at post-baseline visit – baseline NYHA class). Baseline will be defined as the latest NYHA measurement prior to study drug. The possible range of values for change in NYHA is +3 (deterioration in health status) to -3 (improvement in health status). A positive change would indicate deterioration in health from baseline and a negative change would indicate an improvement in health from baseline.

The possible values of NYHA class at a visit are as follows:

- Class I coded as 1
- Class II coded as 2
- Class III coded as 3
- Class IV coded as 4

To compare the change in NYHA class from baseline for a pair of patients, the latest common post-baseline study visit that both patients had a non-missing NYHA result will be compared. In the event the change in NYHA from baseline between a pair of patients is identical, a score of 0 (inconclusive) will be assigned to both patients.

Additional details:

• If a patient did not have any post-baseline information (eg, no information on survival status and no post-baseline data regarding NYHA), then the patient will be inconclusive for all comparisons.

Version: 1.0

Alnylam Protocol No. ALN-TTRSC-004

Secondary endpoint: Change in overall summary score (KCCQ) from Baseline

Step 1: Comparison based on time to death

This comparison will use the same assumptions as stated for the co-primary endpoint.

Step 2: Comparison change in overall summary score from baseline

Definition of change in overall summary score from baseline: Change in overall summary score from baseline is defined as: (overall summary score at post-baseline visit – baseline overall summary score). Baseline will be defined as the latest overall summary score measurement prior to study drug. The possible range in change in overall summary score is -100 (deterioration in health status) to +100 (improvement in health status). A negative change would indicate deterioration in health from baseline and a positive change would indicate an improvement in health from baseline.

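### The SAP's KCCQ and NYHA joint rank tests rank survivors on raw change and make no direct use of the same measure's baseline; the tests are valid but give up a modest amount of efficiency, and for NYHA the SAP strata differ from the protocol's

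*Protocol*

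**What the plan says.** Both documents use a joint rank test for these two endpoints. Protocol 9.2.3.2 says "change in NYHA class and change in KCCQ, will also be compared across treatment groups using stratified Finkelstein and Schoenfeld Joint Rank Tests". The SAP gives the steps after time to death. For NYHA (7.6.2.2) it is "Step 2: Compare change in NYHA from baseline to the latest common study visit", and for KCCQ (7.6.2.3) it is "Step 2: Compare change in overall summary score at the latest common study visit". SAP Appendix I defines both changes as simple differences from baseline.

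The documents differ on strata. Protocol 9.2.3.2 says "Analyses will be stratified using the stratification parameters that are used for randomization", and Protocol 3.1 names those factors: "Treatment groups will be balanced at randomization for NYHA classification (I and II versus III), TTR mutation (V122I versus other FAC mutations), and 6-MWD". SAP 7.6 says "analyses will be stratified based upon a subset of stratification parameters used for randomization: TTR mutation (V122I versus other FAC mutations), and 6-MWD", which leaves NYHA out.

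Neither document gives baseline KCCQ any role beyond forming the difference. By contrast, the serum TTR co-primary is adjusted for baseline TTR (Protocol 9.2.3.1, SAP 7.6.1.3), and the 6-MWD sensitivity MMRM (SAP 7.6.1.2) has a baseline-by-visit term. Beyond the joint rank tests, SAP 7.6.2.2 and 7.6.2.3 plan only shift tables and descriptive statistics.

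**The concern.** Subtracting the baseline does not remove its influence. A patient who starts badly tends to show a better change through regression to the mean, and bounded scales add to this. NYHA class IV is excluded at entry (Protocol 4.2), so a class I patient can only move 0 to +3 and a class III patient only -2 to +1. KCCQ is bounded at 0 and 100. Pairs of survivors with different baselines are thus ranked partly on where they began. That adds noise, and chance imbalance in a placebo arm of about 60 stays in the comparison.

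NYHA and KCCQ are second and third in a fixed sequence. If the composite of CV mortality and CV hospitalization succeeds, a miss on either one ends formal testing of CV mortality, CV hospitalization and all-cause mortality. The plan states no power for either endpoint.

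**Working it through.** **1. The plan's own power figure.** Protocol 9.1 gives 90% power for 6-MWD with 120:60, an effect of 0.55 SD, and 18-month deaths of 20% (placebo) and 13% (active). The two-sided 0.05 level is in SAP 2.3. A simulated joint rank test with exponential deaths and a normal outcome gives 88.2 to 88.5% unstratified, which is close to the stated figure. It gives 86.5% with four equal random strata and 84.4 to 84.7% with eight. Side checks: 0.55 × 70 = 38.5 m (stated 39); ln(0.87)/ln(0.80) = 0.62 (stated 0.6); 180/0.9 = 200. The same design is used below. The KCCQ and NYHA inputs are assumptions because the documents give none.

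**2. Link between change and baseline.** Let ρ be the correlation of baseline with the month-18 score. With equal spread at both times, corr(change, baseline) = r = -√((1-ρ)/2). This gives -0.32 at ρ = 0.8 and -0.50 at ρ = 0.5.

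**3. Gain with no deaths.** Var(adjusted change)/Var(raw change) = 1 - r² = (1+ρ)/2.
- r = -0.3: 1 - 0.09 = 0.91, efficiency 1/0.91 = 1.10.
- r = -0.5: 1 - 0.25 = 0.75, efficiency 1/0.75 = 1.33.

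Deaths dilute this. With full follow-up, both members of a cross-arm pair survive with probability 0.80 × 0.87 = 0.70. About 30% of such pairs are therefore settled at step 1 and never use the score.

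**4. Gain with the plan's deaths.** Relative efficiency is (mean z adjusted / mean z raw)², for an effect of 0.4 SD of change and a continuous score, with the adjustment made at step 2 only.

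| Death hazard per SD of worse baseline | Efficiency, r = -0.3 to -0.5 | Equivalent extra patients out of 180 |
|---|---|---|
| unrelated | 1.06 to 1.21 | 0.06 × 180 = 11 to 0.21 × 180 = 38 |
| 1.5-fold | 1.02 to 1.14 | 4 to 25 |
| 2-fold | 1.00 to 1.11 | 0 to 20 |

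**5. The same in power for KCCQ.** Assumed effect 0.45 SD of change, death unrelated to baseline, SAP strata, with the 6-MWD stratum correlated with baseline KCCQ.

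| ρ | raw | adjusted |
|---|---|---|
| 0.5 | 76.1% | 83.0% |
| 0.7 | 75.5% | 79.7% |
| 0.8 | 76.2% | 78.5% |
| 0.9 | 75.1% | 76.6% |

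**6. NYHA.** An illustrative latent model cut into classes, death unrelated to baseline.

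| ρ | SAP strata, raw to adjusted | Protocol strata, raw to adjusted |
|---|---|---|
| 0.5 | 67.2% to 75.3% | 67.1% to 70.2% |
| 0.7 | 77.1% to 81.9% | 75.3% to 76.7% |
| 0.8 | 84.4% to 86.3% | 80.7% to 81.4% |

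Adjustment gains about 2 to 8 points under the SAP strata and about 1 to 3 under the protocol strata. Adding the NYHA stratum does not itself raise power here: raw power under eight strata is equal to or below that under four.

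**7. Type I error.** Under the null (ρ = 0.6, 15% deaths in both arms), rejection is 5.3% raw and 5.2% adjusted.

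**The case against.** The strongest objection is that the gain depends on death being unrelated to baseline. Protocol 1.4 itself calls NYHA class and 6-MWD predictive of heart failure outcomes. A poor baseline then predicts death (worst rank), while among survivors it predicts a better change (better rank), so the two effects oppose. This stands, and it is why the table in step 4 has three rows. It also bears on the form of adjustment. Regressing the whole joint rank score on baseline, deaths included, yields only about 1.00, 1.00 and 1.02 at the 2-fold hazard (r = -0.3, -0.4, -0.5). Adjusting change at step 2 yields about 1.00, 1.04 and 1.11.

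Second, the SAP strata are not free of baseline information. Protocol 1.4 treats walk distance and NYHA as related, so the 6-MWD stratum already captures some of it. This stands in part; the KCCQ runs in step 5 allow for such a link and still show a gain.

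Third, the unadjusted joint rank test is used throughout the plan, including for 6-MWD, and the TTR ANCOVA has no death tier to compare with. This also stands: adjustment here is an improvement and not a correction.

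Three stronger readings are tempting and not supported:
- **The tests are biased or invalid.** They are not; randomization protects them, and type I error is about 5% either way.
- **Baseline NYHA is ignored by the plan as a whole.** Under Protocol 9.2.3.2, pairs are compared within NYHA I/II or III. Only the SAP omits this, and it openly describes its strata as a subset, without giving a reason.
- **A miss on these endpoints threatens the main result.** The co-primaries are unaffected, and both endpoints are tested only after the composite succeeds.

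**Conclusion.** The point holds as a modest, optional efficiency gain, together with a protocol-SAP difference that needs reconciling. For KCCQ it applies under both documents. For NYHA it applies fully under the SAP strata and only slightly under the protocol strata.

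For a continuous score such as KCCQ, relative efficiency runs from about 1.00 to about 1.21. It depends on the change-baseline correlation (assumed -0.3 to -0.5) and on how strongly baseline predicts death (assumed none to 2-fold per SD). The documents give neither, nor an effect size for KCCQ or NYHA. The continuous-score figures do not carry over to NYHA, which has four classes and many ties; its figures in step 6 are illustrative only. If baseline is weakly related to change, or strongly predicts death, there is little or no gain and at most about a 1-point loss of power, within simulation noise.

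**What to change.** In SAP 7.6.2.2, 7.6.2.3 and Appendix I:

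1. Leave the time-to-death step unchanged.
2. At step 2, compare baseline-adjusted change. For each scheduled visit, regress change on the same measure's baseline with both arms pooled and treatment not in the model. Then compare the two patients' residuals at their latest common visit, keeping the planned stratified test and variance.
3. Keep the unadjusted test as a prespecified sensitivity analysis.
4. For NYHA, either restore the NYHA I/II versus III stratum named in the protocol or justify its omission, and make the two documents agree. The power loss from thin strata (step 6) would be a legitimate reason to give.
5. For NYHA, state openly that adjustment will separate some pairs that the present rule scores as tied, such as two unchanged patients who started in different classes.

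The cost is a few lines of SAP text, one extra programming step and a slightly less direct description of who did better in a pair. No new data are needed. The change should be made before any unblinded analysis. Protocol 9.2 leaves the SAP open until database lock, and SAP 7.8 already foresees an update for the futility criteria.
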